3.4 Randomization

The NIH Clinical Center (CC) Pharmacy will perform randomization. The randomization schedules will be constructed by an independent statistician and shared with the NIH CC Pharmacy. The PI and study staff will not view the randomization schedule *a priori*. Subjects will be randomized as they enter the protocol as follows: The PI or study staff will notify the NIH CC pharmacy of the eligible enrolled participant and the pharmacy will assign the intervention arm according to the predetermined randomization schedule.

3.5 Study Agents/ Intervention

Three study agents will be used: metformin standard release 850mg oral tablet, BiomeBliss® powder, and placebo powder. Metformin will be used within the approved dosing regimens. BiomeBliss will be used according to its labeled instructions, see package label (Appendix C)

Blinding of the investigators and participants will be maintained throughout until the end of the study with the exception of our research nurse who can communicate with participants about any problems with the powder they may be taking. Investigators will be unblinded in the case of a participant needing to be withdrawn due to metformin intolerance; if the intolerance is noted during treatment with placebo, participants will be offered the option to immediately enter the second phase.

The following placebo was chosen to ensure appropriate blinding and similar sensory characteristics for the placebo and product: the placebo (Gatorade G2 (low sugar) powder, a mix of Glacier Freeze and Grape flavors The placebo will be formulated and packaged by NIH Clinical Center Pharmacy as outlined in the Table 2 below and based on the following justifications:

- 1. The non-fiber carbohydrate content and calories are comparable in the placebo and BiomeBliss. Although the total carbohydrate content is different, the calories provided, and the non-fiber carbohydrate content are similar between placebo and Biomebliss. It was important to ensure that there was no fiber in the proposed placebo because the fiber (beta glucan and inulin) is the active ingredient under study. We expect that the placebo should have no impact on stool consistency or frequency, so that we can best evaluate the effect that the study fiber supplement has on the stool.
- 2. Comparable non-nutritive sweetener (NNS) in placebo and BiomeBliss. The proposed placebo is sweetened with a non-nutritive sweetener rather than by sucrose alone to help keep the mass of each dose similar and isocaloric. We expect that stevia (a "natural" NNS) and the artificial NNSs, such as sucralose and acesulfame, will have comparable but negligible effects on glycemia in the short term [40]. However, we acknowledge that the effects of NNS on the microbiome is an emerging area of research. The data on the effects of non-nutritive sweeteners and their potential alterations of gut microbiota are controversial. Over the last decade, there is an increasing number of rodent and in vivo models indicating modest changes in gut phyla with NNS doses that far exceed the maximum acceptable daily intake [41-45]. The clinical impact of these changes is still unclear; human studies are scarce and conflicting. A handful of clinical trials, using acesulfame do not agree on whether this sweetener exerts a change in gut microbiota [46-48]. To our knowledge, there are no

human trials rigorously evaluating gut microbiome with stevia and sucralose [49]. Additionally, we expect that during the phase 2 when we expect to see changes in the microbiome, our participants will be consuming NNS in possibly higher quantities in their usual diet. We will be asking them to avoid diet sodas and other items known to be sweetened principally with NNS (see appendix G), but even foods that are not advertised as "diet" or low-sugar frequently contain NNS, so they will be impossible to avoid in a real-world study.

	BiomeBliss	Gatorade G2 Placebo Mixture
		(4g Grape + 15g Glacier Freeze)
Calories per serving	60kcal (27g)	63 kcal (19g)
Ingredients	Inulin, Blueberry Extract, Beta-glucan (oats), Soy Protein Isolate, Pomegranate Flavor, Xanthan Gum, Citric Acid, Stevia Extract	Glacier Freeze: sugar, citric acid, salt, sodium citrate, natural flavor, monopotassium phosphate, modified food starch, calcium silicate, sucralose, acesulfame potassium, blue 1 Grape: sugar, citricacid, salt, sodium citrate, monopotassium phosphate, natural and artificial flavor, cornstarch calcium silicate, sucralose, acesulfame potassium, blue 1, red 40
Dietary Fiber	9g	None
Total Carbohydrate	22g	17.5g

Table 2:	Biome	Bliss ar	nd G2	Placebo	Nutrition	Facts
	Dionic	Dii35 ui		I IUCCOC	Hatiltion	1 4010

The NIH CC Pharmacy and the prebiotic fiber will be packaged and dispensed in a similar container. Each product will be mixed in a pre-specified shake, provided by the study team, immediately prior to consumption. Mixing the powders with the shake prior to consumption will assure that consistency is also similar.

17.5g

3.5.1 Dose titration for gastrointestinal intolerance

13g

Non-fiber

Carbohydrate

At the start of each period, participants will take metformin 850mg daily, regardless of their dose prior to beginning the study. Participants will be titrated up to 850mg twice daily within 1-3days of Period 1 and 2. For participants who experience intolerable gastrointestinal side effects, metformin dose will be decreased by 850mg. Examples of such side effects include 3 or more diarrheal episodes or intense discomfort or cramping for more than 3 hours. If gastrointestinal symptoms resolve x 2 days, and at the discretion of the PI, the dose of metformin may be increased again to 850mg twice daily. Participants who are unable to tolerate 850mg daily will come for the rescue visit and be withdrawn from the study.

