Visit 5: Participants will bring a stool sample and study medications and have identical assessments as described in visit 3 above. They will also be reminded about keeping food records, which they will be asked to do prior to visit 6

Phase 2 (open-label study and Visit 6)

At the end of Visit 5, patients will leave with a 1-month supply of metformin and MM, to continue taking twice daily, as well as an accelerometer device daily for 4 weeks. **Final study Visit 6** – Participants will undergo assessments as outlined in Table 1 and receive counseling on resuming their medication regimen from prior to the study, as well as follow up nutrition counseling on healthy diet and lifestyle practices.

Rescue visit for GI intolerance

If participants are unable to tolerate 850mg twice daily during the study, they will be withdrawn from the study and have the option come in for a rescue visit, where they will provide a stool sample and obtain bloodwork. They will then be offered the opportunity to enter the open label arm using BiomeBliss® in combination with their highest tolerable metformin dose.

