8.5.2 Evaluation of Risks

This research protocol will be associated with greater than minimal risk. The specific risks and our approach to minimize these risks are outlined below.

- Blood Sampling: Peripheral blood draws (venipuncture) performed during this study for research will not exceed 10.5 mL/kg, or 550 mL (whichever is smaller) per 8-week period for adults. For pediatric patients, blood draws will not exceed 5 mL/kg in a single day, or 9.5 mL/kg or 550 mL (whichever is smaller) per 8-week period. The total blood volume for this study is 372 ml over the 9-week period. Patients may experience some discomfort at the site of the needle entry, and there is a risk of bruising at the site. There is a remote risk of fainting or local infection.
- 2. Intravenous Catheter Placement: The placement of intravenous catheters can be uncomfortable and pose the potential risk of bleeding, bruising and infection. All catheters will be placed under sterile conditions and universal precautions will be observed. Should any complications occur, they will be addressed immediately.

3. Risk associated with metformin

- i. Gastrointestinal upset: Nausea, vomiting, diarrhea, flatulence, abdominal discomfort and indigestion are common side effects associated with metformin use. To be eligible for this study, participants will have an indication to start metformin as first line therapy for type 2 diabetes, if they are not already taking it prior to the start of the study. The following actions will be taken to minimize the risk for gastrointestinal disturbance:
 - a. Metformin dosing will be dose escalated over a 1-3-day time period
 - b. Gastrointestinal symptoms will be recorded daily by participants and communicated with the study team with each submission of the online questionnaire.
 - c. Participants who experience severe and/or recurrent gastrointestinal symptoms, defined as ≥ 3 diarrheal episodes or intense discomfort or cramping > 3 hours, will be withdrawn from the study.
- ii. Boxed Warning Lactic acidosis (rare): The risk of lactic acidosis with metformin use is increased in elderly individuals with renal dysfunction or congenital heart failure. Participants with chronic renal or heart failure, or other chronic metabolic illnesses will not be recruited for this study.

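### On metformin 850 mg twice daily, one GI event calls for dose reduction in section 3.5.1 and for withdrawal in sections 8.5.2 and 9.3.1, with no stated order between them

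*Combined protocol and SAP*

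**What the plan says.** Section 3.5.1 deals with GI intolerance by titration: "For participants who experience intolerable gastrointestinal side effects, metformin dose will be decreased by 850mg". It then illustrates what counts: "Examples of such side effects include 3 or more diarrheal episodes or intense discomfort or cramping for more than 3 hours". If symptoms settle for two days, and at the investigator's discretion, "the dose of metformin may be increased again to 850mg twice daily". The section closes with: "Participants who are unable to tolerate 850mg daily will come for the rescue visit and be withdrawn from the study".

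Section 8.5.2, on metformin risk, takes a different course. "Participants who experience severe and/or recurrent gastrointestinal symptoms, defined as" at least three diarrheal episodes or "intense discomfort or cramping > 3 hours, will be withdrawn from the study". Section 9.3.1 defines severe GI intolerance to metformin or the prebiotic by the same threshold. It gives this as an example of an adverse event leading to withdrawal, under a lead-in that refers to the investigator's opinion.

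Section 3.2, under the rescue visit, says: "If participants are unable to tolerate 850mg twice daily during the study, they will be withdrawn from the study", after which they "have the option come in for a rescue visit" and are offered open-label treatment at their highest tolerable metformin dose. Section 3.5 says that investigators are unblinded when a participant must be withdrawn for metformin intolerance. It mentions immediate Phase 2 entry only for intolerance that arises on placebo.

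Section 5.2 compares the one-week mean tolerability score with a linear mixed model, using baseline score, period and sequence.

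**The concern.** A participant cannot be both kept on a lower dose and withdrawn for the same event. Staff have to choose a section, and two staff members could choose differently while each follows the protocol.

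The event is also close to the primary outcome, which is built from stool consistency, urgency, bloating and flatulence. The choice settles whether the participant stays, whether investigators learn the assignment, how much metformin lies behind the score for that week, and, when the event falls in Period 1, whether there is a second period to compare with. Section 5.1 needs 10 completers from about 20 recruits, so individual cases matter. These are also safety instructions in a study that enrols minors.

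**Working it through.** **The sections side by side**, for a participant on 850 mg twice daily who meets the threshold:

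| Section | Label for the event | Action |
|---|---|---|
| 3.5.1 | intolerable (threshold given as examples) | reduce by 850 mg; may go back up |
| 8.5.2 | severe and/or recurrent (defined by the threshold) | withdraw, no qualifier |
| 9.3.1 | severe intolerance (defined by the threshold) | withdraw, under an investigator-opinion lead-in |

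The labels differ but the operational threshold is the same. No section says to reduce first and withdraw later. On once-daily dosing the conflict disappears: a decrease of 850 mg leaves no metformin, and the sections converge on withdrawal.

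**Secondary differences**

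- The untolerated dose tied to withdrawal is 850 mg twice daily in 3.2 and 850 mg daily in 3.5.1, with no stated order between the two.
- The rescue visit is optional in 3.2 and stated as something that will happen in 3.5.1.
- Open-label entry after intolerance has no treatment limit in 3.2, while 3.5 mentions it only for intolerance on placebo.

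**The plan's own figure.** The plan gives no figure for this event. Its only allowance for withdrawals is in 5.1: 10 / (1 - 0.50) = 20, which reproduces. It is not split by cause.

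**Illustration for one participant**

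Inputs:
- Period length L = 7, 8 or 9 days (3.1, Table 1), assumed equal in both periods.
- First twice-daily day s = 2, 3 or 4, from 1 to 3 days of escalation (3.1).
- Event on day t of Period 1, with s ≤ t ≤ L - 1.
- Assumption: once-daily dosing from day t + 1.

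Planned tablets in a period = (s - 1) + 2(L - s + 1):

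| L | s = 2 | s = 3 | s = 4 |
|---|---|---|---|
| 7 | 13 | 12 | 11 |
| 8 | 15 | 14 | 13 |
| 9 | 17 | 16 | 15 |

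Planned treatment diary days in Phase 1 = 2L = 14 to 18.

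1. Reduction without re-escalation (3.5.1), if 850 mg daily is then tolerated. Tablets lost = L - t. Smallest share: L = 9, s = 2, t = 8 gives 1/17 = 6%. Largest: L = 9, s = 2, t = 2 gives 7/17 = 41%. All diary days and Period 2 are kept.
2. Reduction with re-escalation after two symptom-free days, assuming symptoms resolve at once. Twice daily resumes on day t + 3, which must be no later than L, so exactly 2 tablets are lost: 2/17 = 12% to 2/11 = 18%. Slower resolution means more loss.
3. Withdrawal on day t (8.5.2, 9.3.1). Diary days observed = t of 2L, so 2 to 8 days: 2/18 = 11% to 8/18 = 44%. Period 2 is not observed.

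The case L = 7, s = 3, matching the day-3 step in 3.2, gives 12 planned tablets. Reduction without re-escalation loses 1/12 = 8% to 4/12 = 33%. Withdrawal leaves 3 to 6 of 14 diary days.

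One caveat applies to the extremes. A 7-day supply plus 15% (3.5.2), counted at twice daily, is 14 × 1.15 = 16.1 tablets, so the 17-tablet case slightly exceeds it. The 7-day case does not depend on this.

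**The case against.** The best defence is that the sections describe different grades of severity and leave room for judgement: 3.5.1 offers examples and 9.3.1 refers to the investigator's opinion. This softens the clash between those two. It does not remove it, because 9.3.1 still names this event as one that leads to withdrawal. It does not help with 8.5.2, which has no such qualifier and attaches a single definition to its combined label, so the word recurrent does not imply a sequence. The conflict is sharpest between 3.5.1 and 8.5.2.

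A reader might infer that 3.2 and 3.5.1 flatly contradict each other on the untolerated dose. The documents do not support that. Section 3.5.1 does not say that only those who cannot tolerate 850 mg daily are withdrawn. Reduction and possible rechallenge, followed by withdrawal if twice daily is still not tolerated, is a possible joint reading. What stands is that this order is not written down.

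A reader might also infer that the silence of 5.2 on partial or missing periods comes from this conflict. It does not. That detail is missing under any withdrawal rule, and withdrawals also arise for other reasons, such as hyperglycemia or pregnancy. A linear mixed model can use incomplete pairs, and 5.1 allows for 50% attrition. The silence therefore does not carry this point.

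Finally, a reader might infer a biased treatment effect. The documents give no rate for an event at this threshold and no effect of dose reduction on the score, so neither the size nor the direction of any bias can be stated.

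**Conclusion.** The point holds as a contradiction in the text and should be corrected before the plan is used. At the shared threshold, a participant on twice-daily metformin is reduced and kept under 3.5.1, withdrawn under 8.5.2, and withdrawn subject to the investigator's opinion under 9.3.1. The plan cannot be followed as written for that participant. The differences over the untolerated dose, the rescue visit and open-label entry are secondary.

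The percentages show what the choice of section means for one participant's data, not an effect on the estimate. They rest on equal period lengths, a dose change on the day after the event, and, for the reduction arm, tolerance of 850 mg daily afterwards. The need to reconcile the sections does not depend on them.

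**What to change.** Reconcile sections 3.2 (rescue visit), 3.5, 3.5.1, 8.5.2 and 9.3.1 so that the same GI event cannot lead to conflicting actions, and so that they agree on three further matters: the untolerated dose that means withdrawal, whether the rescue visit is optional, and who may enter open label after intolerance. Which clinical rule applies is for the sponsor to decide.

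Once the rule is settled:

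- Record the date of each dose reduction and each GI withdrawal. The pill counts in 3.5.3 give the percentage taken per period but not the date of a change.
- Report both by treatment and period.
- State in 5.2 how reduced-dose days, and periods cut short by GI withdrawal under that rule, enter the mixed model.

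The cost is wording in five places, a sentence or two in 5.2 and a date field. No visits or participants are added.

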3.5.2 Dispensing and Storing Study Medications

The NIH CC Pharmacy will acquire and store metformin and BiomeBliss® powder for the study and will formulate and compound the placebo powder. The study medication will be coded and dispensed by the NIH CC Pharmacy. The

pharmacy will dispense the study medication according to the predetermined randomization table. The Randomization section contains additional details on the processes we will use to assign randomization. The storage of medications will be according to the package insert for each study drug. Medication will be supplied in 7 day +15% supply at Visit 2 and 4.

3.5.3 Compliance and Adherence

When potential participants are considering participation, the importance of compliance with the intervention assignment will be stressed. The ability to adhere to the protocol of the study, and take medication twice daily, as instructed, is one of the inclusion criteria of the study. Medication adherence will be determined by study personnel counting of pills and sachets that were dispensed at each medical visit and returned at the next medical visit (Visits 3 and 5). The percent of pills and sachets taken over each intervention period will be assessed. We will employ the following strategies:

- 1. Fifteen-percent extra of metformin tablets and powder sachets will be given to the participant to improve compliance, as the participants will not be told how many extra doses are sent (although they will be told that there are more than the exact number of pills so that we can be sure they are taking it). Participants will return the remaining doses and the number of unused tablets/sachets will be recorded.
- 2. Adherence to blood glucose monitoring will be assessed by reviewing CGM or glucometer downloads at every visit.
- 3. The participants will be contacted frequently by text message to encourage and assess compliance. Text and email-based reminders are an important adherence tool which can be tailored to the needs of the individual youth and family. Text messaging has been shown to improve outcomes in children with other chronic diseases, such as asthma ^[50] and sickle cell anemia ^[51] and in adults with type 2 diabetes ^[52].

3.6 Follow-up and Post-Study Treatment

The patient's clinically relevant data, available at the end of the study, will be shared with their diabetes provider with the consent of the participant and the parent. At the family's request, it will also be provided to his or her primary care provider.

Post-Study Obligations

There are no anticipated post-study obligations.

The study drugs (metformin and BiomeBliss®) will only be provided to participants while participating in this protocol. After completion or withdrawal from the study, if the patient would like to continue the medication, their clinically relevant data may be shared with their diabetes provider (with the consent of the participant and the parent) for further management.

4.0 Clinical and Laboratory Methods

4.1 Microbiome Analysis

Fecal samples will be collected in sterile cryovials and stored at 4C for less than 24 hours. The sample will be transferred to -80C and stored until further analysis for microbial diversity and phylla. This analysis will be performed in collaboration with [name] at Wakeforest University. After thawing of fecal sample, fecal DNA will be isolated for microbial compositional analysis using PowerSoil® DNA Isolation Kit or comparable kit. Amplicon sequencing using next generation technology (bTEFAP®) will be used to for microbial sequencing using Illumina MiSeq and HiSeq platforms technologies. In brief, the 16S universal Eubacterial primers 27F AGAGTTTGATYMTGGCTCAG and 519R GTNTTACNGCGGCKGCTG will be utilized to evaluate the microbial ecology of each sample on the Illumina MiSeq with methods via the bTEFAP® DNA analysis service. A single-step 30 cycle PCR using HotStarTaq Plus Master Mix Kit (Qiagen, Valencia, CA) will be used under the following conditions: 94C for 3 minutes, followed by 28 cycles of

94C for 30 seconds; 53C for 40 seconds and 72C for 1 minute; after which a final elongation step at 72C for 5 minutes will be performed. Following PCR, all amplicon products from different samples will be mixed in equal concentrations and purified using Agencourt Ampure beads (Agencourt Bioscience Corporation, MA, USA). Samples will be sequenced utilizing the Illumina MiSeq chemistry following manufacturer's protocols.

The Q25 sequence data derived from the sequencing process will be processed using a pipeline (MR DNA, Shallowater, TX). Sequences will be depleted of barcodes and primers then short sequences < 200bp are removed, sequences with ambiguous base calls removed, and sequences with homopolymer runs exceeding 6bp removed. Sequences are then denoised and chimeras removed. Operational taxonomic units (OTU) will be defined after removal of singleton sequences, clustering at 3% divergence (97% similarity)[53-56]. OTUs will be taxonomically classified using BLASTn against a curated GreenGenes/RDP/NCBI derived database[57] and will be compiled into each taxonomic level into both "counts" and "percentage" files. Count files contain the actual number of sequences while the percent files contain the relative (proportion) percentage of sequences within each sample that map to the designated taxonomic classification.

4.2 Short Chain Fatty Acid Analysis

Fecal samples will be grounded with a pellet pestle motor, followed by being resuspended in 1 mL PBS buffer (0.1 M, pH 7.4). After 4 h dissolution with 1 min vortex every 20 min, samples will be centrifuged (12, 000 g, 10 min) and passed through the 0.45 μ m membrane filter. Cell-free samples were used for determining the concentrations of SCFA (lactate, acetate, propionate and butyrate) using a high-performance liquid chromatography (Waters-2695 Alliance HPLC system, Waters Corporation, Milford, MA, USA) with DAD detector at 210 nm, equipped with a Aminex HPX-87H column (Bio-Rad Laboratories, Hercules, CA). Sample (10 μ L) will be injected each time and H₂SO₄ (0.005 N) will be used to elute the column with a flow rate of 0.6 mL/min at 35°C.

